The level of PA will be measured with the short version of IPAQ questionnaire (Mäder, Martin, Schutz, & Marti 2006). Participants will be asked to estimate the amount of days and spend time for vigorous, moderate and walking activities during the past seven days. To assess the fruit and vegetable consumption during the past seven days, four items will be used. Participants will be asked to count the number of consumed portions or glasses fruit and vegetable a day. It will be distinguished between fruit, fruit/vegetable juice, cooked or steamed vegetable, and raw vegetable (Rafferty, Anderson, McGee, Miller, 2002).

4. Variables related to health

Compensatory health beliefs will be measured by 4 items with Cronbach's α = 0.55. (Knäuper, Rabiau, Cohen, & Patriciu, 2004). **Quality of life:** Respondents will be firstly asked about their general quality of life as "How would you rate your quality of life?", then 7 items in physical health subdomain will be used. (Cronbach's α = 0.89). (WHOQOL-BREF; World Health Organization, 1993).

Statistical analysis:

Data analysis will be performed using SPSS 21.0. Descriptive statistics will be used to describe the baseline characteristics in the study. We will assess whether there are significant differences between the intervention groups compared to the control group according to physical activity and nutrition by means of linear regression analysis in PASW.

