Please think about your typical weeks, did you engage in physical activity at least 5 days per week for 30 minutes or more (or 150 minutes during the week), in such a way that you were moderately exhausted?

1. No, and I do not intend to start.....
2. No, but I am considering it.....
3. No, but I seriously intend to start.....
4. Yes, but only for a brief period of time.....
5. Yes, and for a long period of time.....

2. Physical activity behaviour

We are interested in finding out about the kinds of physical activities that people do as part of their everyday lives. The questions will ask you about the time you spent being physically active in the last 7 days. Please answer each question even if you do not consider yourself to be an active person. Please think about the activities you do at campus, such as, to get from place to place, and in your spare time for recreation, exercise or sport.

Think about all the vigorous activities that you did in the last 7 days. Vigorous physical activities refer to activities that take hard physical effort and make you breathe much harder than normal. Think only about those physical activities that you did for at least 10 minutes at a time.

(1). During the last 7 days, on how many days did you do vigorous physical activities like heavy lifting, digging, aerobics, or fast bicycling?

_____ days

No vigorous physical activities

(2). How much time did you usually spend doing vigorous physical activities on one of those days?

_____ hours per day

_____ minutes per day

Think about all the moderate activities that you did in the last 7 days. Moderate activities refer to activities that take moderate physical effort and make you breathe somewhat harder than normal. Think only about those physical activities that you did for at least 10 minutes at a time.

(1). During the last 7 days, on how many days did you do moderate physical activities like carrying light loads, bicycling at a regular pace, or doubles tennis? Do not include walking.

_____ days

No moderate physical activities

(2). How much time did you usually spend doing moderate physical activities on one of those days?

_____ hours per day

_____ minutes per day

Think about the time you spent walking in the last 7 days. This includes at work and at home, walking to travel from place to place, and any other walking that you have done solely for recreation, sport, exercise, or leisure.

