(1). During the last 7 days, on how many days did you walk for at least 10 minutes at a time?

_____ days

No walking

(2). How much time did you usually spend walking on one of those days?

_____ hours per day

_____ minutes per day

3. How high do you perceive your risk that at some point in the future ...

	Very unlikely			Moderately unlikely			Very likely
1. ... your levels of cholesterol will be too high	 ₁	 ₂	 ₃	 ₄	 ₅	 ₆	 ₇
2. you will suffer a heart attack	 ₁	 ₂	 ₃	 ₄	 ₅	 ₆	 ₇
3. ... your blood pressure will be too high	 ₁	 ₂	 ₃	 ₄	 ₅	 ₆	 ₇
4. ... you will suffer a stroke	 ₁	 ₂	 ₃	 ₄	 ₅	 ₆	 ₇
5. ... you will develop a heart disease	 ₁	 ₂	 ₃	 ₄	 ₅	 ₆	 ₇

4. Intention of physical activity

Which intentions do you have for the near future?

I intent to do for at least 30 minutes a day on minimum 5 days a week (or at least 150 minutes a week)...

	not true			exactly true
1. ... perform strenuous physical activity (heart beats faster, sweating)	 ₁	 ₂	 ₃	 ₄
2. ... be moderately physically active (not fatiguing, mild sweating)	 ₁	 ₂	 ₃	 ₄
3. ... be mildly physically active (hardly strenuous, no sweating)	 ₁	 ₂	 ₃	 ₄

5. Outcome expectancies of physical activity

If I am physically active 5 days a week for 30 minutes or more, then...

	Totally disagree				Totally agree

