1. ... this is good for my health.	 ₁	 ₂	 ₃	 ₄	 ₅
2. ... I feel better afterwards.	 ₁	 ₂	 ₃	 ₄	 ₅
3. ... it will cost me a lot of time (e.g. changing clothes, reaching the sport venue).	 ₁	 ₂	 ₃	 ₄	 ₅
4. ... this will be a financial burden.	 ₁	 ₂	 ₃	 ₄	 ₅

6. Self-Efficacy of physical activity

Motivational Self-Efficacy

I feel certain that I can be physically active a minimum of 5 days a week for 30 minutes, ...

	Totally disagree				Totally agree
1... even if it is difficult.	 ₁	 ₂	 ₃	 ₄	 ₅

Maintenance Self-Efficacy

I feel certain that I can be physically active permanently a minimum of 5 days a week for 30 minutes, ...

	Totally disagree				Totally agree
2... even if it takes a lot of time till I am used to it.	 ₁	 ₂	 ₃	 ₄	 ₅
3... even if I have worries and problems (e.g. proposed date and time).	 ₁	 ₂	 ₃	 ₄	 ₅

Recovery Self-Efficacy

I feel certain that I can again be physically active a minimum of 5 days a week for 30 minutes, ...

	Totally disagree				Totally agree
4... even if I changed my concrete plans several times.	 ₁	 ₂	 ₃	 ₄	 ₅
5... even if I was not physically active for several weeks.	 ₁	 ₂	 ₃	 ₄	 ₅

7. Plans of physical activity

For the next month I already planned in detail ...

	Totally disagree				Totally agree

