7. How satisfied are you with your ability to perform your daily living activities? ₁ ₂ ₃ ₄ ₅
8. How satisfied are you with your capacity to work? ₁ ₂ ₃ ₄ ₅
-

Part IV Demographic factors

1. Your name: _____
2. Please indicate your sex: male/female
3. How old are you? _____
4. Body height: _____ cm; Body weight: _____ kg
5. Please indicate your marital status
 - Single
 - Close relationship, not living together
 - Close relationship, living together
 - Marital partnership/Common law marriage
6. Please indicate your study year.
 - Year 1
 - Year 2
 - Year 3
 - Year 4
7. Please indicate the name of your university
 - Wuhan University
 - Nantong University

亲爱的同学:

您好!

我们本次调查旨在了解您的健康状况和一些与体育运动行为、健康饮食行为相关的影响因素。您对以下调查所作的回答，并无正确和错误之分，我们只需要您的**真诚**回答。

下面呈现的问卷包含了四个方面的内容（1）体育运动行为和相关因子；（2）健康饮食行为和相关因子；（3）与健康状况有关的变量；（4）人口统计学变量。请仔细阅读每份问卷，并按要求回答。

感谢您的合作!

第一部分 体育运动行为及相关因子

1. 体育运动的阶段变化

您是否会进行每周至少 5 次，每次至少 30 分钟的中等强度体育运动？请您根据平时的情况进行选择。

- 1 我没有做到，也并未打算这样.....
- 2 我没有做到，但正考虑这样.....
- 3 我没有做到，但真的很想这样.....
- 4 我能够做到，但只持续了很短的时间.....
- 5 我能够做到，并且长期这样.....

2. 体育运动行为

我们想了解人们日常生活中会进行哪些体育运动。下述问题意在获悉您在过去 7 天所进行的体育运动情况，即使您认为自己不是一位积极参加体育运动的人，也请认真回答下面的每道题目。您所参加的可以是与学习有关的一些活动，也可以是在闲暇时从事的体育娱乐活动，可以在寝室或室外空地上进行的，也可以是在两地往返的过程中进行的（例如步行或者骑自行车往返）。

请您回想一下在刚刚过去的 7 天里，您所进行过的大强度的体育运动（非常消耗体能且呼吸明显比平时急促）每次持续时间至少为 10 分钟

- (1). 在这 7 天里，您有几天进行过大强度体育运动（例如，负担重物、大强度有氧运动、快速骑自行车等）？

_____ 天

我没有进行过大强度体育运动。

- (2). 您进行一次大强度体育运动的持续时间通常为多少？

_____ 小时/每天

_____ 分钟/每天

请您回想一下在刚刚过去的 7 天里，您所进行过的中等强度体育运动（适中的体能消耗，呼吸较平时略有急促）每次持续时间至少 10 分钟。

- (1). 在这 7 天里，您有几天进行过中等强度体育运动（例如，搬运较轻的物品、中等速率骑自行车、网球双打，但不包括散步）

_____ 天

我没有进行过中等强度体育运动。

- (2). 一次中等强度体育运动的持续时间通常为多少？

_____ 小时/每天

_____ 分钟/每天

请您回想一下在刚刚过去的 7 天里，您所进行过的低强度体育运动，例如，步行往返于两地，或者以休闲娱乐/体育锻炼为目的的散步。

(1). 在这 7 天里，您有几天进行过每次持续至少 10 分钟的散步？

_____ 天

我没有散步

(2). 每次散步的持续时间通常为多少？

_____ 小时/每天

_____ 分钟/每天

3. 下面的问题涉及到您对疾病的危险感知。请思考一下，您的身体今后出现下面问题的可能性有多大。请选择最符合您情况的选项。

	绝对 不会			有可能			完全 可能
1. 发生高脂血症的可能性	 1	 2	 3	 4	 5	 6	 7
2. 心脏病急性发作的可能性	 1	 2	 3	 4	 5	 6	 7

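### The attached Chinese form may miss walking between places, and two of its activity self-efficacy items differ in meaning from the English form

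*Combined protocol and SAP*

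**What the plan says.** In the application, Measures (3. Past health Behaviour) says activity will be measured with the short IPAQ, as days and time for "vigorous, moderate and walking activities during the past seven days".

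The English questionnaire (Part I, 2) introduces walking as including "walking to travel from place to place, and any other walking that you have done solely for recreation, sport, exercise, or leisure". It then asks "on how many days did you walk for at least 10 minutes at a time" and "How much time did you usually spend walking on one of those days". Its moderate-activity item tells students to leave out walking.

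The Chinese questionnaire (Part I, 2) gives as examples in its walking stem "步行往返于两地，或者以休闲娱乐/体育锻炼为目的的散步": walking between two places (步行), or strolling for leisure or exercise (散步). The day item is then "您有几天进行过每次持续至少 10 分钟的散步", with 散步 only.

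For activity self-efficacy (Part I, 6), the second English item, on maintenance, reads "even if it takes a lot of time till I am used to it". The fourth, on recovery, is about having changed one's concrete plans several times. The Measures section gives each of these subscales two items per behaviour.

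**The concern.** The Chinese stem treats 步行 and 散步 as two different things and then asks only about the second. A student who follows the wording can report no walking while walking to class every day. Walking is one of three components of the activity measure. Activity is a dependent variable in the planned MANCOVA for Objective 2, with baseline behaviour as covariate. If an intervention raises activity through everyday walking, the form could miss part of that change.

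Self-efficacy is a dependent variable in the planned MANOVA. With two items per subscale, one altered item carries much of the score. The activity and diet subscales then share a name but not the same content.

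**Working it through.** There is no sample-size, power or alpha figure to reproduce here. The check is a comparison of the two language forms (glosses of the Chinese are mine), followed by simple arithmetic.

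**Side by side**

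| Element | English form | Chinese form |
|---|---|---|
| Walking stem | Travel between places, plus leisure or exercise walking | Low-intensity activity, for example 步行 between places, or 散步 for leisure or exercise |
| Day item | Walking | 散步 |
| None box | No walking | No 散步 |
| Duration item | Walking time on one of those days | Usual time of each 散步 (每次), with boxes in hours and minutes per day |
| Exclusion in moderate item | Walking | 散步 |
| Activity maintenance item 2 | Time needed to get used to it | It will use up a lot of my time |
| Activity recovery item 4 | Changed concrete plans | Changed the type of exercise |
| Diet maintenance item 2 | Time needed to get used to it | Same meaning kept |
| Diet recovery item 4 | Changed concrete plans | Same meaning kept |

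The Chinese vigorous and moderate duration items also ask about a single session (一次) above per-day boxes, so the per-occasion wording is not confined to walking.

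**Possible loss of walking minutes.** The inputs are assumed, because the documents give no walking data. Take a student who walks 20 minutes between places on 7 days and strolls 30 minutes on 2 days.

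- All walking, as in the English form: 20 × 7 + 30 × 2 = 140 + 60 = 200 minutes a week.
- Chinese items read narrowly: 30 × 2 = 60 minutes a week, a loss of 200 − 60 = 140.
- Chinese items read in the light of the stem: 200 minutes a week, a loss of 0.

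For this student the loss lies between 0 and 140 minutes a week.

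**Per-occasion wording.** Suppose the 20 minutes are two 10-minute trips a day, and the student counts them. Days times time per day gives 7 × 20 = 140. Days times time per occasion gives 7 × 10 = 70, half the total.

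**Self-efficacy.** One altered item out of two is 1/2 = 50% of each subscale if items are weighted equally; the scoring is not stated. Across maintenance and recovery, 2 of 4 activity items changed meaning, against 0 of 4 diet items.

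**The case against.** The strongest reply on walking is that students read the stem first. It names walking between places, and the introduction to the section also mentions travelling on foot. Many may take 散步 as shorthand for everything in the stem. This stands: the documents cannot show how students will read the word, so omission is possible and not certain.

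A reader might also infer that walking between places will be recorded as moderate activity, because the exclusion names only 散步. The form gives little support for that. Its stem calls such walking low intensity, and its moderate item requires somewhat faster breathing. At most, brisk walking is ambiguous.

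A reader might infer that the two altered items no longer measure self-efficacy. That goes too far. The Chinese stems still ask about confidence to keep going and to do it again; what changed is the barrier named. The maintenance item does now sit close in wording to the time-cost item under outcome expectancies, but that item asks about cost, not about persisting despite it. No planned analysis compares activity scores with diet scores.

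The form may also be a draft. The application template asks for a draft questionnaire, and Step 1 of the Validation stage provides for adjusting materials. That makes Step 1 the right place for the correction, but it does not ensure one. Step 1 asks two students about their understanding and describes no comparison of the language versions. A student can understand 散步 perfectly and still answer a narrower question. The pilot was in cardiac rehabilitation patients, and the Cronbach's alphas reported under Measures show internal consistency, not whether an item keeps its intended meaning.

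**Conclusion.** The wording differences are real and worth correcting before launch. As attached, the Chinese form allows walking between places to be left out, wholly or not at all depending on the reader. It asks walking time in a unit that does not match its answer boxes. It also changes the barrier in one of the two items of each activity subscale for maintenance and recovery self-efficacy.

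The effect on Objective 2 cannot be sized. The share of students affected is unknown, and the plan does not say how walking minutes enter the activity score.

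It is tempting to infer that the arm comparison is biased. The documents do not support that: all three arms are measured with the same electronic questionnaires at each time point. The expected harm is measurement error in the outcome and its baseline covariate, with weaker validity and sensitivity.

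The conclusion assumes that students answer the Chinese form. No sentence says so, but the two mainland sites and the student-addressed Chinese version make it the natural reading.

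**What to change.** In Step 1 of the Validation stage, before launch:

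- Use 步行, stated to include both travel and leisure, in both walking items, the none box and the moderate-activity exclusion.
- Ask walking duration per day, to match the answer boxes, and make the same edit in the vigorous and moderate duration items.
- Retranslate activity self-efficacy items 2 and 4 to mirror the Chinese diet items (Part II, 5, items 2 and 4).
- Check the whole Chinese form item by item against the English and record the result.

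This takes a few words on an electronic form, within the validation work scheduled for months 1–9. It should be done before T1, because a later change would break the repeated measures. The downside is that these items will differ from the cardiac pilot version. The pilot alphas for activity maintenance (0.64) and recovery (0.75) self-efficacy will then no longer apply exactly, and should be re-estimated from the T1 data.
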